Landspatientregisteret (LPR) is a national and clinical database administered by the Danish Health Authority since 1976. All information generated when a patient is treated by the public health service is reported here. In addition to information regarding procedures and admissions, the register contains information on residence, partner status, level of education, income, comorbidities and emigration amongst others. Operations are recorded according to the NOMESCO classification, while diagnoses are coded according to the ICD-10 classification.

Identification of primary procedures

We will determine the cohort of primary procedures from DKR (called P-DKR) by identifying all primary procedures performed from January 1st 1998 to December 31st 2021. P-DKR is then transferred to Danmarks Statistik (DS). Through DS, all primary procedures in the observation period will be identified using NOMESCO operation codes (KNGB*) and these will be collected in a cohort called P-SD. P-DKR and P-SD will be joined into a cohort called PRIM and this cohort will best describe all primary procedures performed in Denmark during the observation period.

Identification of revision procedures

The DKR cohort of revisions (R-DKR) will be identified by all registrations marked as revisions during the observation period. R-DKR is also transferred to DS. All revisions will be identified in DS as R-DS using the NOMESCO operation codes KNG* (knee procedure), KNGC* (revision of knee), KNGG* (arthrodesis) and KNFQ19 (femur amputation). The cohorts R-DKR and R-DS will be combined and called REV. This cohort will best describe revision procedures performed in Denmark during the observation period.

Insertion of cement spacers presents a special registration problem, as different registration practices exist. Some use KNGS codes (eg KNGC59A – Insertion of spacer in a knee joint in connection with revision). We intend to not consider spacer insertion as a revision. For example a two-stage revision will be considered as one revision.

Organization of data

A table (G) with PRIM and REV will be created. G will contain information on revisions, deaths, disappearances, emigration and the associated dates. For each knee joint in PRIM and for each date in the observation period, it will be possible to describe the status of the knee joint.

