In the event of a discrepancy between data from DKR and DS, data from DKR will be chosen, but specific rules will be created for specific situations. In case of missing data for indication for revision (for example if a procedure is not registered in DKR), DS diagnosis codes will be used.

Data is obtained from both registers, as the degree of completeness is very high in both registers. By combining data a near-perfect data collection of the population is ensured.

Description of data from DKR

The Regions' Clinical Quality Development Program (RKKP) manages data from DKR. After receiving approval from PACTIUS, RKKP was queried for data-extraction. Data has since been acquired. Data consists of primary and revision procedures performed from January 1st 1998 to December 31st in 2021. The data includes information regarding:

CPR-number (personal identification number)

Sex

Hospital

Department

Laterality of procedure

Height

Weight

Revision (yes/no)

Indication for procedure

Operation date

Type of arthroplasty

Femur fixation (Cement, yes/no)

Tibia fixation (cement, yes/no)

Femur component

Tibial component

Patella component (yes/no)

Patella fixation (cement, yes/no)

Femur stem (yes/no)

Tibia stem (yes/no)

Operating room

Use of tourniquet (yes/no)

Use of drain

Number of previous revisions

Indication for revision

First revision date

Description of data from LPR

Danmarks Statistik contains many registers about the population in Denmark, including registers regarding place-of-residence, income, education, partner-status, as well as Landspatientregisteret, which contains all information created when a patient is admitted to a public hospital. DS also contains information regarding all treatments performed in privately owned hospitals.

An application has been submitted regarding the acquisition of data from primary and revision arthroplasties performed from January 1st 1998 to December 31st 2021. The requested variables are as follows:

Name

Social Security number

Address

Changes of residence, including information on movements, emigration, disappearance, death

Income

Diagnoses/comorbidities

Operations with operation code: KNGB*, KNGC*, KNGG* and KNFQ19

Level of education

Partner status

Employment status

Statistics

After extraction of data, pooling of data in DS, creation of the populations and tables as described in the previous section on data extraction, statistical analyzes will be carried out.

WPA1

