## 1. STUDY OVERVIEW

---

**Background and rationale** Knee arthroplasty is a common procedure performed worldwide to improve the quality of life for patients with degenerative knee conditions, trauma, and tumours. Complications can occur after knee arthroplasty, which may lead to a revision procedure, where at least one implant is exchanged, added, or removed. As the number of primary procedures in the world is increasing, so is the corresponding number of revisions. Some patients may require additional revision procedures, and some may end in a negative spiral of repeated revisions; We define three or more revisions on the same knee as being 'multiply revised'. The clinical impression of multiply revised patients is that the repeated occurrence of complications has significant impacts on the patients' quality of life including chronic pain, decreased independence, and increased morbidity. No study has yet investigated the incidence and prevalence of multiply revised knee arthroplasty patients stratified by previous revisions. To improve the care of multiply revised patients, epidemiological information is required which is the rationale of this study.

**Objectives** The aim of this observational study is to investigate the incidence and prevalence of multiply revised knee arthroplasty patients in all Danish patients with primary knee arthroplasty.

**Hypothesis** The number and burden of knee arthroplasty revision procedures and patients in Denmark has increased dramatically in the last 23 years.

**Methods** This is an observational study. Data will be collected from all primary and revision knee arthroplasties performed in Denmark from January 1st 1998 to 31st December 2021. Data will be acquired from two registers: The Danish Knee Arthroplasty Register (DKR), containing surgeon-reported data on primary and revision knee arthroplasties. In addition, data will be acquired from Landspatientregisteret, which contains all clinical data collected during any visit to a public or private healthcare facility in Denmark.

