### PICOTS

**Population:** All Danish citizens who have received a primary knee arthroplasty at a Danish healthcare facility, from the 1st of January 1998 to the 31st of December 2021

**Intervention/Exposure** Multiple revision knee arthroplasties in the same knee

**Comparator:** None

**Outcome (primary):** Annual standardized prevalence and incidence of n-grade revisions following knee arthroplasty between 1998 and 2021 in Denmark.

**Time:** Retrospectively, from the 1st of January 1998 to the 31st of December 2021, i.e., up to 24 years follow-up.

**Study design:** Observational retrospective register study.

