#### **Data management, for both registers.**

Definition of a revision: A revision is defined as the exchange, addition, or removal of a knee prosthesis component (1). However, knee arthrodesis and amputation are not included in this study.

Definition of major revision: A major revision is defined as exchange of the femoral component and/or the tibial component with subgroups of tibial, femoral and all component exchange (2).

Definition of minor revision: A minor revision is defined as the exchange of polyethylene liner and/or addition or revision of the patella component. Insertion/removal/exchange of spacers are also included in this category (2).

Population: The population is defined as the number of alive citizens in the state of Denmark. Annual populations are defined as the population in Denmark on the 1st of January that year. Additional data for sex and age of the population is acquired. Data for the population is acquired from Danmarks Statistik (3).

In case of disagreement between registers: In cases of discrepancy between the two registers, Landspatientregisteret will overrule the Danish Knee arthroplasty register concerning following variables:

- Laterality
- Date of surgery
- Gender
- Age
- Performing institution

In cases of discrepancy between the two registers, the Danish Knee arthroplasty register will overrule Landspatientregisteret concerning following variables:

- Procedure code
- Revision of tibia
- Revision of femur
- Indication

Calculation of standardized prevalence: Annual standardized prevalence is calculated as the number of patients living with a n-grade revision during a given year as a proportion of the population in Denmark (the 1st of January that year) (3). The prevalence is then multiplied by 100,000 for standardization. This is done for each level of revision, each year. E.g., the standardized prevalence for 1998 is calculated as:

$$\text{Standardized prevalence, 1998} = \frac{\text{Number of knees living in 1998 with a } n - \text{ grade revision}}{\text{Total population in Denmark in 1998}} * 100,000$$

The prevalence is only calculated for revisions performed between January 1st 1998 and December 31st 2021.

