#### 4. PROTOCOL DEVIATIONS WITH BEARING ON THIS STATISTICAL ANALYSIS PLAN

---

The following details in this SAP represent deviations from the protocol.

Header in the protocol	Change	Reason
(currently no deviations)		

[figure not shown]

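### On a side conflict the SAP lets LPR overrule DKR without checking which knee has a recorded primary: an undeclared departure from the protocol's default that can lower revision grades

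*SAP*

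**What the plan says.** SAP section 3, under data management for both registers, divides the variables between the registers. For one group, "In cases of discrepancy between the two registers, Landspatientregisteret will overrule the Danish Knee arthroplasty register concerning following variables"; the group is laterality, date of surgery, gender, age and performing institution. DKR prevails on procedure code, tibial and femoral revision, and indication. No exception is given for laterality.

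The protocol, under Organization of data, starts from the other side: "In the event of a discrepancy between data from DKR and DS, data from DKR will be chosen" (DS is Danmarks Statistik, through which LPR data are obtained). The sentence continues: "but specific rules will be created for specific situations". SAP section 4, the table of protocol deviations, reads "currently no deviations".

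The unit of grading is the knee. SAP section 1 says "We define three or more revisions on the same knee as being 'multiply revised", and the prevalence formula in section 3 counts knees in its numerator. The protocol's status table is also built by knee: "For each knee joint in PRIM and for each date in the observation period", where PRIM is the cohort of identified primaries. The SAP population, by contrast, is defined by person: "All Danish citizens who have received a primary knee arthroplasty at a Danish healthcare facility".

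**The concern.** If grade is counted per knee, the recorded side decides which knee a revision belongs to and what grade every later revision on that knee receives. A fixed register hierarchy ignores the most useful evidence in a side conflict, namely which knee had a prosthesis to revise.

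One wrong side lowers the true knee's count for the rest of follow-up. The chance of at least one such error rises with the number of revisions, so the effect is largest at grade 3 and above, the group the study is about. The SAP plans no sensitivity analysis on side and no count of side conflicts, so the published tables would not show how often this happened.

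**Working it through.** **1. The texts side by side.** The protocol makes DKR the default and allows rules for particular situations. The SAP makes LPR prevail for five variables in every situation. Even if the SAP list is read as the promised rules, the default is reversed for those five and section 4 is empty.

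**2. The rule applied to one patient.** Take a patient with one prosthesis, in the right knee. For a revision on that knee DKR says right and LPR says left. Under the SAP rule the revision goes to the left knee, which has no primary. The readable text does not say what follows: the revision may be excluded, as the PRIM-based table suggests, or counted as grade 1 on the left. Either way the next revision on the right knee is graded one too low. In a bilateral patient the same error adds a revision to the other replaced knee, so one knee is graded too low and the other may be graded too high.

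**3. Share of revisions that lose their grade.** The documents give no figure to reproduce. Let q be the share of revision records that the rule puts on the wrong side, assumed independent between records. A true grade-n revision keeps its grade on its own knee if all n records are correctly sided, so the share lost is 1-(1-q)^n.

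| q (assumed) | n = 1 | n = 3 |
|---|---|---|
| 0.25% | 0.25% | 1-0.9975^3 = 0.7% |
| 1% | 1.0% | 1-0.99^3 = 3.0% |
| 2% | 2.0% | 1-0.98^3 = 5.9% |

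For n = 5 at q = 1% it is 1-0.99^5 = 4.9%.

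**4. Effect on the reported count at grade 3 and above.** This needs the chance of going from one grade to the next. As an illustration, use the 20% per grade that the protocol's Background cites from an English register (over differing horizons), with at most six revisions per knee.

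- Revisions at grade 3 or above, per knee that reaches grade 3: 1 + 0.2 + 0.04 + 0.008 = 1.248.
- All revisions on such a knee: 2 + 1.248 = 3.248.
- In a patient with one replaced knee, each wrong-sided record on such a knee costs one revision at grade 3 or above. To first order the proportional loss is q × 3.248/1.248 = 2.60q, that is 0.65% at q = 0.25%, 2.6% at 1% and 5.2% at 2%.

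**5. What a check against the primary recovers.** With one replaced knee whose primary is recorded on the right side, the check removes the whole loss. With two replaced knees it cannot help. If 30% of patients were bilateral (assumed), 0.6/1.3 = 46% of replaced knees would belong to them. The check would then settle the other 54% of wrong-sided records. The remaining loss at q = 1% would be at most about 0.46 × 2.6% = 1.2%, taking both primaries to precede the revision.

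**The case against.** - **The protocol foresaw specific rules.** The SAP's split by variable can be read as those rules, so it goes too far to call it a plain contradiction of the protocol. This stands. What remains is that the default was changed and section 4 does not say so.
- **Nothing says that a misplaced revision drops out.** A reader might infer this from the population definition, but that is written per person, and the patient in the example stays in the population. The exclusion flow diagram is not shown. Exclusion is only one of two possible outcomes. The lower grade on the true knee follows under both.
- **LPR may be the better register on side.** A reader might infer that the SAP chose the wrong register. No text supports that. A mis-sided DKR record would do the same harm under the protocol's default, and the formula would apply to it with its own q. The point is therefore the missing check, whichever register leads.
- **A general data check is planned.** SAP section 3 says that analysis variables will be screened for outliers and inconsistencies, and a revision on a knee without a primary could be caught there. But that text gives no rule for resolving what is found, and it does not override the stated hierarchy.
- **The effect may be small.** This is fair. The study is descriptive, a steady share of misplaced records would hardly change a relative trend over time, and the per-patient sum in SAP Figure 3 is unaffected when the revision stays with the same patient. The absolute counts at high grades, which are a main result, are still exposed.

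**Conclusion.** The point holds as a modest but worthwhile correction. The SAP gives LPR precedence on laterality with no check against the knee's primary, this departs from the protocol's default, and the departure is undeclared. Those statements need no assumption.

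The size does. It rests on an assumed q, which is narrower than the discordance rate because it covers only conflicts in which LPR is the register in error. It also rests on independence between records. Over q from 0.25% to 2%, between 0.7% and 5.9% of true third revisions lose their grade. The loss in the grade 3 and above count is slightly smaller. Most of it is avoidable in patients with one replaced knee and much less in bilateral patients. The documents do not support a claim that DKR should simply take precedence.

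**What to change.** In SAP section 3, replace the laterality rule for revisions. When the registers disagree on side, assign the revision to the side with an earlier recorded primary if exactly one side has one; otherwise apply the stated hierarchy. In addition:

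- State how a revision on a knee without a recorded primary is handled.
- Report the number of side conflicts, how each was resolved, and the number of revisions on knees without a recorded primary.
- Repeat Tables 2 and 3 and Figure 2 under the plain LPR rule and with DKR laterality, as sensitivity analyses.
- Enter the changed hierarchy in SAP section 4.

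The cost is a short text change, one conditional step in the linkage and two reruns of the tables. Patient key, side, date and the primary/revision distinction are already in the SAP's variable list.

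The new rule has its own weak points. It carries an error forward where the primary is itself mis-sided. It can also override a correct record where the true knee's primary predates 1998, and so is not recorded, while the other knee has a later primary. The reported counts and the two sensitivity analyses would show how much either could matter.

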There is a paucity of studies investigating multiple revised patients. Deere et al. investigated the subject in 2019, containing just over 30,000 patients from the English register NJR(8). The study found that 20% of those revised for the first time were revised a second time after 13 years. 20% of those were revised for the third time after 5 years, and 20% of those were revised again for the fourth time within 3 years. The risk of multiply revisions was higher in men and in younger patients. Also, the study found that the risk of revision increased as time between revisions decreased.

In 2010, Ong et al. investigated the risk of revision after primary and first revision after total knee arthroplasty (TKA) and total hip arthroplasty (9). The study contained data from 73,000 primary knee arthroplasties, and 1600 revisions performed between 1997 and 2006. The study found that the risk of a second revision was 6 times higher than the risk of a first revision. See **Figure 3**:

Figure 3: Graph illustrating risk of revision after primary and first revision. From Ong et al.

In 2021, Belt et al. investigated the association of the indication for revision and the risk of re-revision (10). The study found that the cumulative re-revision rate was 19% after 8 years (significantly higher than the cumulative revision rate after primary knee arthroplasty). Klasan et al. found that the re-revision rate after revision due to aseptic loosening was 12% over a 16-year period (1999-2015) in New Zealand (11). In 2018, Postler et al. examined a smaller population of 300 patients in a prospective, single-centre study (12). The study found that re-revisions were performed 4 years since the last revision, while first revisions were performed after 8 years since primary knee arthroplasty.

A Danish study was performed in 2022, by Arndt et al. which investigated rate of re-revision after revision for either “aseptic resolution” or “pain without resolution” (13). The study included data from 4299 revisions from 1997 to 2018 from the Danish Knee Arthroplasty Register. The study found a cumulative revision rate of 23% after 20 years for patients with pain without loosening. For patients with aseptic loosening, the cumulative revision rate after 20 years was 19%.

No study has investigated the cumulative revision rates stratified by number of previous revisions in a national population. It is not known how many patients live with a revision

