- 1) What is the annual incidence of revisions of various degrees, and how has the incidence changed during the last 20 years?
- 2) What is the current prevalence of n-grade revisions, and how has the prevalence changed during the last 20 years?
- 3) What is the relationship between the annual incidence of revisions of n-grade with the incidence of primary procedures in the preceding years?

WP-A2: Cumulative Revision Rates (CRR)

The purpose of this WP is to determine the cumulative revision rate (CRR) for revisions of different grades (number of previous revisions) to generate information that can be used for informing patients preoperatively.

Research questions:

1. What is the CRR for n-grade revision?
2. Is CRR influenced by demographic and surgical variables such as sex, age, education, implant type, place of residence, income, operative technical conditions and the indication of revision such as infection, aseptic loosening, instability, pain without reason?

WP-A3: Lifetime risk of multiple revisions

The purpose of this WP is to determine the lifetime risk of revision of various grades as well as the lifetime risk of arthrodesis and amputation. These risks will be investigated in relation to demographic and surgical variables.

Research questions:

1. What is the lifetime risk that a patient with a given combination of demographic and surgical variables will need n-number of revisions after primary arthroplasty?
2. As above but with arthrodesis and amputation as the risk event.

Review of literature

To gather relevant background information for this protocol, MEDLINE via pubmed was searched to find relevant literature in the field. The MESH words "knee replacement" and "reoperation" were used. We wanted to identify articles that either described epidemiological findings regarding multiple revision knee arthroplasties or described risk factors associated with repeated revisions. There were no MESH words containing "rerevision", "multiply revisions" or "repeated revisions".

Articles found: 4350 results.

Based on the title, this number of abstracts were reviewed: 97

Of the abstracts, so many articles were reviewed and read: 65

Number of articles used in the protocol: 47.

Material and methods

Design

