## 2. TABULAR PRESENTATION OF TIMING OF OUTCOME MEASUREMENTS

---

Registry	Observation period	Variables relevant for this study
The Danish Knee Arthroplasty Register	January 1 st 1998 – 31 st December 2021	ID-key (number) Date of surgery (date) Code for implant type (number) Revision performed (yes/no) Revision of tibial component (yes/no) Revision of femoral component (yes/no) Laterality (left/right) Sex (male/female) Age (number) Indication for primary procedure (number) Performing institution (number) Duration of procedure (minutes)
Landspatientregisteret	January 1 st 1998 – 31 st December 2021	ID-key (number) Date of surgery (date) Code for procedure (number) Laterality (left/right) Sex (male/female) Age (number) Performing institution (number) Year of death or emigration (date)

---

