#### Definition of minor revisions in Landspatientregisteret

Minor revisions are defined as the KNGC codes listed here:

KNGC02A: Secondary insertion of only polyethylene liner in uncemented partial prosthesis in knee  
KNGC09: Secondary insertion of uncemented partial prosthesis in knee without specification  
KNGC1: Secondary insertion of cemented partial prosthesis in knee  
KNGC12A: Secondary insertion of only polyethylene liner in cemented partial prosthesis in knee  
KNGC22A: Secondary insertion of only polyethylene liner in uncemented total prosthesis in knee  
KNGC23: Secondary insertion of patellofemoral component in uncemented total prosthesis in knee  
KNGC32A: Secondary insertion of only polyethylene liner in hybrid total prosthesis in knee  
KNGC33: Secondary insertion of patellofemoral component in hybrid total prosthesis in knee  
KNGC42A: Secondary insertion of only polyethylene liner in hybrid total prosthesis in knee  
KNGC43: Secondary insertion of patellofemoral component of cemented total prosthesis in knee  
KNGC59: Secondary insertion of interpolated prosthesis in knee  
KNGC59A: Insertion of spacer in knee in connection with revision  
KNGC99A: Secondary insertion of patella component  
KNGS49: Incision or revision with placement of medication in case of infection in knee joint

Laterality: Code for specifying right/left knee. TUL1 = right, TUL2 = left

Sex: Specifying the sex of the patient. M = male, F = female

Age: Number specifying the age of the patient at the time of the performed procedure

Performing institution: Code specifying the performing institution. The codes are classified as SHAK-codes, developed by "Sundhedsdatastyrelsen". (<https://medinfo.dk/sks/brows.php>)

Year of death: The year in which the patient has died. The patient will be marked as "ALIVE" if death has not occurred at the end of the observation period.

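### Prevalence puts a whole-year numerator over a 1 January population; read literally it exceeds current prevalence and can place one knee in two grades

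*SAP*

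**What the plan says.** SAP section 3 (Data management, for both registers) defines annual standardized prevalence as the "number of patients living with a n-grade revision during a given year", taken as a proportion of the Danish population and multiplied by 100,000. The worked formula for 1998 changes the unit from patients to knees but still covers the whole year: "Number of knees living in 1998 with a" n-grade revision. The denominator belongs to one day: "Annual populations are defined as the population in Denmark on the" 1st of January of that year.

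The same section limits which revisions count: "The prevalence is only calculated for revisions performed between January" 1st 1998 and the end of 2021. No revised knee can therefore be in the count at the start of 1998, so the SAP's own 1998 example cannot be a 1 January count.

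On leaving the count, the Landspatientregisteret variable list has "Year of death: The year in which the patient has died". The table in SAP section 2 labels death or emigration as a year but types it as a date. Neither place says that a person who leaves during the year is removed, or which grade a knee takes in a year in which it is re-revised.

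The protocol's question for WP-A1 is "What is the current prevalence of n-grade revisions, and how has the prevalence changed during the last 20 years". Its section on organization of data says that the status of each knee can be described for every date in the observation period.

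**The concern.** Current prevalence is a stock on a date. A count over a whole year is that stock plus everyone who left it during the year. For an n-grade knee there are three ways out: death, emigration and the next revision. The third also adds the knee to the next grade, so one knee appears twice in the same year.

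Grade appears to mean current grade. The SAP figure notes report a separate category above grade n for prevalence, and Figure 3 gives each patient a single total. On that reading, adding grade-specific prevalences to obtain the number of multiply revised knees would count some knees more than once.

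Prevalence is half of the primary outcome. The SAP plans no tests and no confidence intervals, so the counting rule alone determines the reported figure.

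**Working it through.** The documents give no prevalence figure, so there is nothing to reproduce. The check is an identity followed by an illustration of size.

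**Identity.** For grade n in year Y, let A be the stock on 1 January, N the entries during the year and X the exits (death, emigration, next revision).

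- Year-end stock: E = A + N - X.
- Count at any time in the year: P = A + N = E + X.

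So P - E = X and P - A = N. The whole-year count is never below the count on either date. If grade n means n or more, a re-revision is not an exit and X contains only deaths and emigration.

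**Inputs from the protocol's background section.** About 13% of primaries are revised within 20 years. From the cited English registry study, 20% are re-revised by 13 years after a first revision and 20% by 5 years after a second; after a third, "20% of those were revised again for the fourth time within 3 years". There were more than 150,000 primaries in 20 years, scaled here to 150,000 x 24/20 = 180,000 over 24 years.

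**Assumptions not in the documents.** Mortality of 2%, 4% or 6% per year; primaries rising linearly; revision times with Weibull shape 1 or 0.6 (the latter weighted to early failure); grade 4 exit equal to grade 3 exit; no emigration.

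**Yearly hazards**, -ln(1 - q)/T:

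- Primary to grade 1: -ln(0.87)/20 = 0.0070
- Grade 1 to 2: -ln(0.80)/13 = 0.0172
- Grade 2 to 3: -ln(0.80)/5 = 0.0446
- Grade 3 to 4: -ln(0.80)/3 = 0.0744

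**Steady state.** X/E is approximately the re-revision hazard plus mortality:

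- Grade 1: 0.0172 + 0.02 to 0.06 = 3.7% to 7.7%
- Grade 2: 0.0446 + 0.02 to 0.06 = 6.5% to 10.5%
- Grade 3: 0.0744 + 0.02 to 0.06 = 9.4% to 13.4%

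**Growing cohort, 1998-2021.** Simulating the six combinations of mortality and shape gives these excesses of the whole-year count over the 31 December 2021 count:

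| Grade | Exclusive grades |
|---|---|
| 1 | 4-8% |
| 2 | 5-10% |
| 3 | 6-13% |
| 4 | 6-10% |

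On the n-or-more reading, the excess is about 2-6% at every grade.

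**One scenario in counts** (shape 0.6, mortality 2%; counts rounded, ratios from unrounded values):

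| Grade | Whole-year count | 31 December | Ratio | Excess knees | Of these, also counted at next grade |
|---|---|---|---|---|---|
| 1 | 10,359 | 9,988 | 1.037 | 372 | 175 |
| 2 | 1,349 | 1,282 | 1.052 | 67 | 43 |
| 3 | 271 | 254 | 1.065 | 17 | 12 |
| 4 | 73 | 69 | 1.062 | 4 | 3 |

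Every grade has the same population denominator, so the excess per 100,000 falls with grade just as the knee counts do. The model produces 9,300-16,100 revisions in total against the protocol's more than 20,000, so only the ratios are of use. The grade 4 ratio rests on few knees.

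**The case against.** Period prevalence is a legitimate measure, and the count is excessive only relative to a point prevalence that the SAP does not name. The SAP never says that a knee counts if it held the grade at any time in the year; that is the literal reading but not the only one. An analyst could count at year end, and the protocol's data table, which holds dates of death and emigration, would allow it. The study is descriptive, its hypothesis is a rise over 23 years, and one rule applied every year leaves the series readable. In the three shape-0.6 scenarios, for instance, the grade 1 excess over year end is 4.3-7.9% in 2005 and 3.7-7.8% in 2021. The restriction to revisions from 1998 onward is a separate influence on the trend.

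Most of this stands as a limit on size and consequence. It does not remove the mismatch. The numerator is not labelled as period prevalence, its denominator belongs to one day, and the protocol asks for the current figure. A year-end count over the 1 January population of the same year would also be mismatched.

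A reader might infer that the outcome is inflated most at the highest grades, the ones the study is about. The documents do not support that without qualification. The rise with grade is proportional only, it levels off between grades 3 and 4 against a 31 December count, and it disappears if grade n means n or more. Against a 1 January 2021 count the model does give a steeper gradient (11-15%, 15-20%, 19-30% and 20-35% at grades 1 to 4), but part of that is real growth of the stock during the year.

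**Conclusion.** The point holds as a cheap improvement. Taken literally, the prevalence rule is a whole-year count over a one-day population. It exceeds current prevalence by the number of knees leaving each grade in the year, and with exclusive grades it counts a re-revised knee twice. That direction follows from arithmetic alone.

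The size is illustrative: single digits to low teens in per cent against a year-end count. It depends on assumed mortality and on re-revision rates from an English registry, not Danish data. For grade 1, assumed mortality supplies most of the excess (0.02-0.06 of a yearly exit rate of 0.037-0.077).

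It would go too far to conclude that the study's hypothesis of an increase is threatened. Nothing here shows that the conclusion about the trend would change.

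**What to change.** In SAP section 3, define prevalence for year Y as point prevalence on 31 December of Y:

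- Assign each knee the single highest grade it has reached by that date.
- Exclude people dead or emigrated by the end of Y. This works even if only the year of each event is held.
- Divide by the population on 1 January of Y+1.
- State one counting unit for each display: knees for Figure 2 and the tables, patients for Figure 3. Reconcile the patient wording with the knee formula.
- State whether grade n is exclusive or means n or more.

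If period prevalence is what is wanted, name it as such, say how deaths, emigration and grade changes within the year are handled, and use a mid-year population.

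The cost of the point-prevalence version is the 1 January 2022 population by sex and age group (earlier years' figures are already in the plan), and a separate prevalence denominator column in Supplementary Tables 1-4, which now share one 1 January 2021 column with incidence. Reported prevalence will be slightly lower. The change does not address the absence of revisions performed before 1998.
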